## II. Data Collection Overview

The following table indicates the necessary case report forms to be completed at the given time point:

Form Name	Enrollment	Operative	Discharge Assessment	1 to 6 Weeks Post-op (+14 days)	3 Months Post-op ( $\pm 30$ days)	6 Months Post-op ( $\pm 60$ days)	1 Year Post-op ( $\pm 90$ days)	Revision
Enrollment Form	X							
Demographic Evaluation	X							
Operative Record		X						
Postoperative Discharge Assessment			X					
VAS Pain				•	•	•	•	
EQ-5D-5L				•	•	•	•	
FIX-IT				X	X	X	X	
X-rays	X	X	X	X	X	X	X	X
Postoperative Follow-up Evaluation				X	X	X	X	
Study Completion		*	*	*	*	*	*	X
**Adverse Event (Complication)	*	*	*	*	*	*	*	X
Protocol Deviation	*	*	*	*	*	*	*	*
Physician Radiographic Assessment (Including RUSH)				*♦	*♦	*♦	*♦	*♦
Explant Device			X	X	X	X	X	X

X Completed by Investigator or Designee (required)
 
 
• Completed by Patient
 
* Completed by Investigator or Designee (as applicable)
 
♦ Independent radiographic review may be performed by Sponsor's designee if requested by the Sponsor.
 
 
** If device related Adverse Event occurs, a Product Experience Report (PER) must be completed and sent to the sponsor as well and include the Operative Report (index and revision) and Radiographs (immediate post-op, all follow-up visits, and pre-revision).
								

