#### **IV. Study Objectives**

The objective of this observational prospective study is to systematically document the clinical outcome of the THP Hip Fracture Plating System when used in fractures of the proximal femur, intracapsular and intertrochanteric fractures, as compared to historical literature data for the same indications when using cannulated or hip screws . These objectives will be assessed using standard scoring systems, radiographic evidence, and adverse event records.

**Safety:** Will be assessed by monitoring the frequency and incidence of adverse events (AE), serious adverse events (SAE), adverse device effects (ADE), serious adverse device effects (SADE), and unanticipated serious adverse device effects (USADE) and device deficiencies.

**Performance:** Will be determined by analyzing the implant survival, overall pain and functional performances on standard scales, subject quality of life, and radiographic parameters of subjects who received the subject device(s). Operative time and readmissions will also be analyzed. Implant survival will be based on removal or intended removal and determined using the Kaplan-Meier method.

- **Overall pain and functional performance** will be based on Visual Analog Scale (VAS) Pain, Rush Score, EuroQol 5D-5L (ED-5D-5L), and Functional Index for Trauma (FIX-IT).
- **Survivorship** will be based on the rate of revision in the study device due to fixation failure or non-union of the femur.
- **Radiographic parameters** to be analyzed may include, but are not limited to, implant fracture, significant implant migration or subsidence, and implant loosening. Other significant findings may also be observed and reported during the course of this study.

It is planned that once sufficient data has been collected allowing meaningful statistical analysis; contributing investigators can use the data for peer reviewed publications, podium presentations and as a basis for surgeon discussions and learning.

**Study Endpoints:** The primary endpoint of this study is defined as the rate of revision after 12 months due to device related complication or non-union of the femur. The secondary endpoints of this study are defined as radiographic and clinical fracture healing of the proximal femur using standard scoring methods.

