## **I. Post-operative Follow-up Procedures (Data Collection)**

Post-operative clinical evaluations/assessments will be conducted at 1 to 6 weeks (+ 14 days), 3 months ( $\pm$  30 days), 6 months ( $\pm$  60 days), and 12 months ( $\pm$  90 days) post-surgery. The following case report forms will be collected at

each interval:

1. Postoperative Follow-up
2. VAS Pain

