3. EQ-5D-5L
4. RUSH
5. FIX-IT
6. X-rays (A/P and lateral views of the hip or pelvis)
7. Physician Radiographic Assessment
8. Adverse Event(s)
9. Protocol Deviation(s)
10. Study Completion
11. Explanted Device

Subjects will be followed post-operatively for 12 months. Unless the study is otherwise closed, data will continue to be collected until the subject completes the study per the protocol, voluntarily withdraws from the study, is withdrawn from the study by the investigator, is lost to follow-up, undergoes revision to remove a study device, (due to complication) including partial removal i.e. screw, or expires. See Management of Incurrent Events for additional details. Reason(s) for study completion must be documented on the Study Completion case report form.

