A study subject will be considered lost to follow-up after they have missed a visit and a reasonable number of attempts to locate and evaluate them have failed. All attempts to contact the subject are to be documented in the subject's medical record and on the **Study Completion** case report form. In particular, the reason for the Study Completion must be documented. Missed visit(s) also must be documented using the **Protocol Deviation** case report form, unless the visit is retrospective.

7. Protocol Deviations

Investigators should not deviate from the study protocol. If a protocol deviation does occur, the deviation must be documented on the **Protocol Deviation** case report form and submitted to the Sponsor. If applicable per their reporting requirements, the Investigator or Designee will also report applicable protocol deviations to their IRB or EC.

8. Study Termination

Study subject participation is expected to end upon completion of the subject's 1 year follow-up visit unless the subject voluntarily withdraws from the study, is withdrawn from the study by the Investigator, is lost to follow-up, undergoes revision to remove a study device, (due to complication) including partial removal i.e. screw, or expires. Reason(s) for study completion must be documented on the **Study Completion** case report form.

If the Sponsor decides to terminate the study early, the Sponsor will inform the Investigators of the reason for early study termination. It is the responsibility of the Investigators to inform their IRB or EC as applicable according to local and national laws/regulations.

9. Modification of the Protocol

All amendments to this clinical protocol shall be agreed to by the Sponsor and be recorded with a justification for the amendment prior to implementation. Approval of the applicable IRB or EC must be obtained prior to implementation, if required according to the local and/or national laws/regulations.

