### **B. Sample Size**

Due to the different historical revision rates for intertrochanteric fractures (~7%) and intracapsular fractures (~20%), study enrollment will be split between the two groups to maintain the integrity of the sample size with an expectant lost to follow-up rate of 15%. Intertrochanteric fractures will be limited to a maximum of 89 enrolled subjects and intracapsular fractures will be limited to a maximum of 101 enrolled subjects. This will provide enough evaluable data for both indications to show the necessary statistical improvement from the historical revision rates. The assumed revision rate of the THP Hip Fracture Plating System is 15% for intracapsular fractures and 5% for intertrochanteric fractures with a non-inferiority margin of 8%.

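### The final visit can close follow-up from about day 275, so 12-month revision status, the primary endpoint, need not be observed for subjects seen early

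*Combined protocol and SAP*

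**What the plan says.** Section IV (Study Objectives) defines the primary endpoint as "the rate of revision after 12 months due to device related complication or non-union of the femur".

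The last scheduled visit is listed in section II (Data Collection Overview) as "1 Year Post-op ( $\pm 90$ days" and in section VIII.I (Post-operative Follow-up Procedures) as "12 months ( $\pm$ 90 days) post-surgery".

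Two passages say when observation stops:
- Section IX.D.8 (Study Termination): "Study subject participation is expected to end upon completion of the subject's 1 year follow-up visit", with earlier exit for withdrawal, loss to follow-up, device removal or death.
- Section VIII.I: "Subjects will be followed post-operatively for 12 months", followed by the rule that, unless the study is closed, "data will continue to be collected until the subject completes the study per the protocol" or leaves for one of those same reasons.

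On analysis, section IV states: "Implant survival will be based on removal or intended removal and determined using the Kaplan-Meier method". Section XI.A repeats Kaplan-Meier for implant survival. Neither section gives an analysis day or a censoring rule, and neither says that the primary rate is the Kaplan-Meier estimate. Section XI.B (Sample Size) sets fixed historical rates, assumed device rates and an 8% margin, and says of the enrolment caps: "This will provide enough evaluable data for both indications".

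**The concern.** The endpoint has a fixed horizon, whereas observation ends at a visit whose date can vary by about six months. A subject whose final visit falls on day 275 has complied with the protocol and is finished. If that subject's fixation is revised on day 300, and the revision was not already intended at the visit, the event lies inside the endpoint period but no provision requires anyone to look for it. Follow-up for 12 months, as section VIII.I promises, is then not delivered.

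A second problem runs the other way. If the primary rate is taken as a crude proportion of subjects revised by their last visit, subjects seen late contribute up to about 15 months of exposure. Such a rate mixes roughly 9 to 15 months of follow-up.

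The study has no concurrent control. Its rates are set against fixed historical figures of about 20% (intracapsular) and 7% (intertrochanteric), so no comparison arm shares the same visit schedule and absorbs the error.

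**Working it through.** **Inputs from the documents.** Window of 90 days either side of 12 months (sections II and VIII.I). Assumed device revision rates of 15% intracapsular and 5% intertrochanteric, enrolment caps of 101 and 89, and 15% loss to follow-up (section XI.B).

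**Inputs assumed.** A 365-day year. The documents give no distribution of revisions over time and no distribution of visit dates, so both are varied below.

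**Step 1: the window.** 365 − 90 = 275 days (275/365 × 12 = 9.0 months). 365 + 90 = 455 days (15.0 months). The largest gap before the endpoint day is 90 days, or 90/365 = 25% of the endpoint period.

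**Step 2: evaluable subjects.** 101 × 0.85 = 85.9, taken as 86. 89 × 0.85 = 75.7, taken as 76. The plan states no alpha or power. With one-sided 5% and 90% power (assumed), a single-proportion formula against the historical rate plus 8 points gives 84.7/0.85 = 99.6, so 100 (plan: 101), and 75.1/0.85 = 88.4, so 89 (plan: 89). The enrolment figures are thus approximately recovered. This does not bear on the gap itself.

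**Step 3: reading of a crude rate under constant hazard.** If p is the true 12-month rate and follow-up stops at day d, the observed rate is 1 − (1 − p)^(d/365).

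| Visit timing | True 15% reads | True 5% reads |
|---|---|---|
| All at day 275 | 11.5% | 3.8% |
| Even over days 275–365 | 13.3% | 4.4% |
| Even over days 275–455, all revisions to the visit counted | 14.98% | 5.00% |
| All at day 455 | 18.3% | 6.2% |

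For example, 1 − 0.85^(275/365) = 0.115. The even-window rows average the same expression over the window.

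In the first row the events missed are 86 × (0.150 − 0.115) ≈ 3.0 intracapsular and 76 × (0.050 − 0.038) ≈ 0.9 intertrochanteric.

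**Step 4: a milder case.** Suppose only 5% to 10% of 12-month revisions fall between day 275 and day 365, and 25% to 50% of subjects are seen at the start of the window. The expected loss is n × p × (share of revisions that are late) × (share of subjects seen early):
- Intracapsular: 86 × 0.15 × 0.05 × 0.25 = 0.16, up to 86 × 0.15 × 0.10 × 0.50 = 0.65 events.
- Intertrochanteric: 76 × 0.05 × 0.05 × 0.25 = 0.05, up to 76 × 0.05 × 0.10 × 0.50 = 0.19 events.

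**Step 5: what Kaplan-Meier would and would not do.** A subject last seen unrevised on day 275 would be censored then, not counted as a 12-month success. If visit timing is unrelated to revision risk, this limits the bias. It does not recover the unobserved revisions, and early visits reduce the number at risk near day 365.

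**The case against.** The best defence is that the only event-rate method in the plan is Kaplan-Meier, that section IV's description of survivorship comes close to the primary endpoint, and that intended removal counts as an implant-survival event. Each follow-up visit includes radiographs and adverse event forms, so many impending revisions would be picked up at the visit. The window is also symmetric, and late visits offset early ones. All of this stands, and it limits the size. It does not close the gap. The primary endpoint is a cause-specific revision rate that the plan does not tie to the implant-survival analysis or to day 365, and revisions not yet foreseen at an early visit remain uncollected.

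Three stronger readings are tempting, and the documents do not support them:
- *Early completers are counted as 12-month non-revisions.* Nothing says so. The reference to evaluable data in section XI.B concerns sample size and is not an analysis rule.
- *The window favours the device.* That holds only if visits run early. Late visits raise a crude rate.
- *The chance of wrongly meeting the limit rises several-fold.* With the true rate at the historical rate plus 8 points and follow-up at day 320, an exact one-sided 2.5% test of a crude proportion would wrongly pass 6.3% of the time instead of 1.6% (n = 86), and 5.1% instead of 2.1% (n = 76). Those figures need constant hazard, mostly early visits, a crude proportion and an alpha that the plan does not state. Section XI describes descriptive summaries and specifies no test.

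**Conclusion.** The concern holds as a defect in data collection. Following the protocol exactly can leave the primary endpoint unobserved for up to the last 90 days of its 12-month period, and the statement that subjects are followed for 12 months conflicts with ending participation at a visit allowed from about day 275. This is more than missing analysis detail, because information not collected before close-out may not be recoverable.

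The size is uncertain and probably small. Under constant hazard it ranges from almost no net bias (visits even over the whole window) to 3.5 points intracapsular and 1.2 points intertrochanteric (everyone seen at day 275). If few revisions fall in months 9 to 12, less than one event per group is lost. It becomes material only if visits cluster early or late revisions are common, and the protocol controls neither. A change to the plan is worthwhile because it is cheap, not because a large bias has been shown.

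**What to change.** Leave the visit window and the sample size as they are, and make three changes:

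1. **Section IV and section XI.** State that the primary rate is the Kaplan-Meier estimate at day 365, by fracture group, with subjects censored at the date of last known revision status and revisions after day 365 excluded from this estimate.
2. **Section VIII.I and section IX.D.8.** For any subject whose final visit falls before day 365, confirm revision and vital status at or after day 365 by chart check or telephone before follow-up is closed.
3. **Reconcile** the 12-month follow-up statement in section VIII.I with the end-of-participation rule in section IX.D.8, so that both describe the same end point.

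The cost is protocol wording plus one short contact or chart check for subjects seen early. Sections V and VIII.G already use chart review as a data source. Minimum observation for a subject who completes the study rises from about 275 to 365 days.

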## ***E. Medical Events/Adverse Events Definitions and Classifications***

An adverse event is any unfavorable or unintended sign, symptom, or disease that impacts the subject. Adverse event is synonymous with complication or medical event.

Adverse events are required to be reported on the **Adverse Event Report** case report form. The completed **Adverse Event Report** case report form must be submitted to the Sponsor in a timely manner. The Investigator or Designee will also promptly provide the Sponsor with any additional requested information required for the Sponsor to comply with regulatory requirements. If applicable per their reporting requirements, the Investigator or Designee will also report applicable adverse event(s) to their IRB or EC.

### 1. Classification of the Event

#### *Adverse Event (AE):*

An adverse event is any unfavorable or unintended sign, symptom, or disease that impacts the subject.

#### *Serious Adverse Event (SAE)(i):*

A Serious Adverse Event is any adverse event that

- a. led to death
- b. led to serious deterioration in the health of the subject, that either resulted in:
  1. a life-threatening illness or injury, or
  2. a permanent impairment of a body structure or a body function, or
  3. in-patient or prolonged hospitalization, or
  4. medical or surgical intervention to prevent life-threatening illness or injury or permanent impairment to a body structure or a body function
- c. led to fetal distress, fetal death or a congenital abnormality or birth defect.

Note: Planned hospitalization for a pre-existing condition, or a procedure required by the protocol, without serious deterioration in health, is not considered a serious adverse event.

#### *Adverse Device Effect (ADE)(i):*

An Adverse Device Effect is an adverse event related to the use of a medical device.

Note 1: This definition includes adverse events resulting from insufficient or inadequate instructions for use, deployment, implantation, installation, or operation, or any malfunction of the medical device.

Note 2: This definition includes any event resulting from use error or from intentional misuse of the medical device.

*Serious Adverse Device Effect (SADE)(i):*

A Serious Adverse Device Effect is an adverse device effect that has resulted in any of the consequences characteristic of a serious adverse event.

The Sponsor is responsible for determining the final classification of adverse events.

If an Unanticipated Serious Adverse Device Effect (USADE) is identified by the Sponsor, it will be promptly reported to concerned Investigators and regulatory authorities as required by applicable regulatory requirements. If applicable per their reporting requirements, the Investigator or Designee will report the USADE to their IRB or EC.

2. Intensity of Symptoms

*Mild:*

The subject is aware of the sign or symptom, but finds it easily tolerated. The event is of little concern to the subject and/or little clinical significance. The event is not expected to have any effect on the subject's overall health or well-being.

*Moderate:*

The subject has discomfort enough to cause interference with or change in usual activities. The event is of some concern to the subject's health or well-being and may require medical intervention and/or close follow-up.

*Severe:*

The event interferes considerable with the subject's usual activities.

The event is of definite concern to the subject and/or poses substantial risk to the subject's health or well-being. The event is likely to require medical intervention and/or close follow-up and may be incapacitating or life threatening. Hospitalization and treatment may be required.

**NOTE:** The term "severe" refers to the intensity of the event and can be used with any event, without regard to whether or not it meets the criteria for being classified as "serious" or "unanticipated". For example, a subject can have a severe headache, but it is not a serious event.

### 3. Outcome Definitions

The outcome is in relationship to the Adverse Event, not the treatment rendered for the event (if any).

*Resolved:*

The adverse event has been resolved and/or no further treatment is required to treat the reported condition or illness.

*Tolerated:*

The adverse event will most likely never be resolved. The subject "tolerates" the illness or condition as a matter of life.

*Pending:*

Treatment or diagnostic studies were prescribed for the adverse event and the outcome of the adverse event is not yet known.

*Study Withdrawal:*

Due to the adverse event, the subject was withdrawn from the study.

*Device Removal:*

The adverse event resulted in the removal of a study device.

*Reoperation of Affected Joint:*

The adverse event resulted in reoperation of the study joint, but the reoperation did not include removal of a study device.

*Death:*

The outcome indicates the subject died as a direct result of the

reported adverse event.

#### **F. Monitoring of the Study**

Prior to initiating the clinical study, the Sponsor may conduct a site initiation visit to ensure the Investigator(s) and study staff understands the study protocol and requirements and have adequate time and resources to implement and conduct the study. Prior to study initiation, the Investigator must have a fully executed CTA and IRB or EC approval of the study protocol and the study Informed Consent.

During the course of the study, the Sponsor will conduct periodic central monitoring and maintain contact with the study staff to monitor compliance and evidence of adverse events, in accordance with the Sponsor's policies and procedures. The Sponsor will address any identified non-compliance with the executed CTA, study protocol, and applicable regulatory requirements.

If onsite monitoring visit(s) are deemed appropriate by the Sponsor, the Investigator will permit representatives of the Sponsor's monitoring team to have direct access to inspect all source data/documents, study documents/binders, study subject case report forms, corresponding sections of study subject medical/hospital records, and any other documents relevant to the study. All Sponsor visits (including site initiation) will be documented using the **Monitoring Visit Log**.

#### **X. Risk Analysis**

This post-market clinical study is classified as minimal risk(ii) and there are no anticipated risks specific to study participation other than the potential loss of confidentiality. There are no experimental procedures in this study, and participation in this study is not anticipated to affect the medical treatment of enrolled subjects.

When used in accordance with product labelling, the risks associated with the use of the THP System are similar to those of standard femoral neck or intertrochanteric fracture treatment system used for the same clinical indication or purpose. Unanticipated adverse events can also occur.

For general surgical risks, please refer to the FDA cleared instructions for use for this product.

## **XI. Statistical Considerations**

Performance of the commercially available THP System for treatment of femoral neck fractures or intertrochanteric fractures will be evaluated for fracture healing, pain, function, quality of life, and survivorship. Data collected in this study will be summarized descriptively and descriptive summaries will be the basis of any study reports issued. These summaries may be used for interim study reports and may also be used to support regulatory submissions, presentations, and/or publications. Additional surgical technique and instrumentation data may be collected and evaluated.

